9.3.4. Pupil Diameter

Pupil Diameter will be measured prior to any cycloplegia using a hand-held pupil card provided to the sites and the result in 0.5 mm increments will be recorded on the eCRF. Descriptive statistics for pupil diameter and changes from baseline at each assessment time point will be presented by randomized treatment. For analysis, the average of the right and left eyes will be used.

9.3.5. Binocular Accommodative Amplitude

Binocular accommodative amplitude will be measured with the participant wearing current refractive correction prior to cycloplegia with a study-specified accommodation near-point rule and results in diopter will be recorded on the eCRF. Descriptive statistics for amplitude and changes from baseline at each assessment time point will be presented by randomized treatment.

9.3.6. Corneal Endothelial Cell Density

Corneal endothelial cell count data will be obtained using specular microscopy at selected sites with the required equipment (approximately 25% of study participants). Three measurements in units of cells/mm² will be obtained for each eye at each visit and analysis will be performed using the mean of the 3 assessments, first averaged by eye, then averaged over both eyes.

Descriptive statistics for the mean central endothelial cell density and changes from baseline at each assessment time point will be presented by treatment group.

9.3.7. Biomicroscopy

Biomicroscopy (with corneal fluorescein staining) will be performed by slit-lamp examination of lids, conjunctiva, cornea, iris and lens evaluated as follows:

- Normal
- Abnormal (not clinically significant [NCS])
- Abnormal with clinical significance (clinically significant [CS])

The number and percentage of participants with at least 1 treatment-emergent clinically significant abnormality for any parameter and for each parameter will be summarized for each treatment group. At each level of summarization, a participant will be counted once even if the participant experiences more than one treatment-emergent clinically significant abnormality summarizing data for the worse eye. For analysis, the worse eye will be defined as the eye with the greater degree of abnormality where Abnormal CS > Abnormal NCS > Normal. An abnormality will be deemed treatment emergent if the onset date is on or after the date of first treatment At Month 36 and Month 48 analyses, findings will be summarized by current treatment at the time of abnormality to visit. Data from all ophthalmoscopy assessments will be listed.

9.3.7.1. Corneal Staining

Corneal staining will be graded as 0 = none, 0.5 = trace, 1 = mild, 2 = moderate, and 3 = severe. The number and percentage of participants for each grade will be summarized via shift from baseline tables for the worse eye for each treatment group. For analysis, the worse eye is the eye with the higher grade. Tables will be presented for baseline to worst visit (defined as highest grade) and baseline to most recent visit for Month 24 and Month 36 analyses. For Month 36 and Month 48, participants will be summarized by each treatment received (e.g., if a participant receives more than one treatment, the participant will be included under each treatment)

In addition, to investigate the recovery of any emergent corneal staining, the above analyses showing the shift from baseline to the most recent visit (e.g., last available visit prior to analysis cut-off) will be performed on the subset of participants who had a post-baseline value of 1 or greater based. Participants will be summarized by the treatment taken at the time of assessment.

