8.3 ADVERSE EVENTS AND SERIOUS ADVERSE EVENTS

8.3.1 DEFINITION OF ADVERSE EVENTS (AE)

The investigator is responsible for reporting all AEs that are observed or reported during the study, regardless of their relationship to study drug.

An **AE** is defined as any untoward medical occurrence in a participant enrolled into this study regardless of its causal relationship to study drug. Participants will be instructed to contact the investigator at any time after randomization if any symptoms develop.

A treatment-emergent AE (**TEAE**) is defined as any event not present before exposure to study drug or any event already present that worsens in either intensity or frequency after exposure to study drug.

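### The SAP's recovery table for emergent corneal staining does not require an increase over baseline, so it mixes children who never worsened with children who worsened and returned

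*SAP*

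**What the plan says.** SAP Section 9.3.7.1 sets the scale: "Corneal staining will be graded as 0 = none, 0.5 = trace, 1 = mild, 2 = moderate, and 3 = severe". It also sets the unit of analysis: "For analysis, the worse eye is the eye with the higher grade". For the Month 24 and Month 36 analyses it plans two shift tables on all children, baseline to worst visit and baseline to most recent visit.

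It then adds a further analysis whose purpose is "to investigate the recovery of any emergent corneal staining". The method is to repeat "the above analyses showing the shift from baseline to the most recent visit" in the "subset of participants who had a post-baseline value of 1 or greater". The sentence runs on for one more word, *based*, and stops there. Nothing in it refers to the baseline grade, and the section defines neither emergent nor recovery for staining.

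Two nearby definitions show what emergent means elsewhere in the documents:

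- SAP Section 9.3.7 (Biomicroscopy): "An abnormality will be deemed treatment emergent if the onset date is on or after the date of first treatment".
- Protocol Section 8.3.1, for treatment-emergent adverse events: an event absent before exposure, or "any event already present that worsens in either intensity or frequency after exposure to study drug".

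**The concern.** The table is meant to answer one question: among children whose staining arose or increased on treatment, how many recovered? The selection rule asks something else, namely whether the child ever had a grade of at least 1 after baseline. A child at grade 1 before dosing and at grade 1 throughout passes that test, although nothing emerged and there is nothing to recover from.

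What is at stake is how the table reads for children with staining at baseline. Their cells would hold two kinds of history, and a reader could not tell which children are the ones the table is about.

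**Working it through.** The plan states no figure here, so there is nothing to reproduce. The check enumerates what the rule admits and where each history lands.

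**Inputs.** Grades 0, 0.5, 1, 2 and 3 (SAP 9.3.7.1). Selection: worst grade after baseline at least 1. Display: baseline grade by most recent grade. Emergent is taken as worst grade above baseline grade.

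**Step 1: is a baseline grade of 1 or more possible?** Yes, by two routes.

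- Protocol Section 5.2 excludes children with ocular inflammation or infection, keratitis included, but sets no limit on staining grade. Protocol Section 8.3.5 does not treat staining of 0.5 or 1+ as an adverse event.
- SAP Section 9 resets the baseline at the start of each treatment for the Month 36 and Month 48 safety summaries. A child who reaches grade 1 on SYD-101, is re-randomized to Vehicle and stays at grade 1 has a Vehicle baseline of 1. That child enters the subset under Vehicle without any change on Vehicle.

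**Step 2: which combinations qualify?** There are 5 baseline grades and 3 worst grades of at least 1, so 5 × 3 = 15 combinations.

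| Baseline | Worst > baseline | Worst ≤ baseline |
|---|---|---|
| 0 | 3 | 0 |
| 0.5 | 3 | 0 |
| 1 | 2 | 1 |
| 2 | 1 | 2 |
| 3 | 0 | 3 |
| Total | 9 | 6 |

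The six without worsening, written (baseline, worst), are (1,1), (2,1), (2,2), (3,1), (3,2) and (3,3). These count possible patterns, not children. The rule also leaves out one emergent pattern, 0 to 0.5, although the stated aim covers any emergent staining.

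**Step 3: where do they land in the shift table?** The most recent grade cannot exceed the worst grade. Counting each possible history once:

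| Cell (baseline, most recent) | Histories with worsening | Histories without |
|---|---|---|
| (1,1) | 2 | 1 |
| (2,2) | 1 | 1 |
| (3,3) | 0 | 1 |

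Cell (1,1) holds the child who was 1 throughout and also the child who went from 1 to 3 and back to 1. Cell (2,2) is mixed in the same way. Cells below the diagonal in the rows for baseline 1 and 2 are mixed too, and the row for baseline 3 contains only children who did not worsen. No history without worsening falls above the diagonal. The rows for baseline 0 and 0.5 contain only emergent histories.

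**Step 4: effect of adding the condition worst > baseline.** The admitted combinations fall from 15 to 9. Cells (1,1) and (2,2) then hold only children who worsened and returned.

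**The case against.** The best reply is that the format already protects the reader. Baseline grade is one axis, so a child at 1 before and 1 after sits on the diagonal and reads as no shift. That stands. A reader might infer that stable pre-existing staining would be reported as drug-related staining that failed to recover, but the documents do not support this. The SAP sets no recovery fraction, and that reading needs recovery to mean a most recent grade below 1 with the baseline axis ignored. If recovery means return to baseline, the same children would count as recovered and the error would flatter recovery.

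The companion table also helps. All cells above the diagonal are emergent. So, within a baseline row, the children who worsened and returned to baseline or lower equal the number with worst > baseline minus the number with most recent > baseline. At Month 24 a careful reader could obtain that total by subtraction. This limits the harm but does not remove it:

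- The reader must combine two tables to answer a question that one of them claims to answer.
- The subtraction does not say which cell the children ended in.
- At Month 36 the two tables are described with different rules for attributing children to treatments, so their rows may not line up.
- Baseline-to-worst tables are listed only for Months 24 and 36.

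Two further replies are fair. The definition in Protocol Section 8.3.1 concerns adverse events, and grade 1 staining is not one; the definition in SAP Section 9.3.7 is closer. A child who was at grade 1 before any treatment and did not change fails both. Also, the sentence is broken, and the missing words may have named baseline. That is a reason to complete it: as it stands, a programmer has only the threshold of 1.

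**Conclusion.** The point holds as a minor one. Followed as written, the rule admits children who never worsened into a table on recovery of emergent staining, and the diagonal cells for baseline 1 and 2 cannot separate them from children who worsened and returned. Rows with baseline 0 or 0.5, and the two shift tables on all children, are unaffected.

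The size cannot be given. If a proportion e of children newly reach grade 1 or more and a proportion s have stable staining of grade 1 or more, the share of the subset that is not emergent is s/(s + e). With e assumed at 6% and s at 1% to 5%, it is 1/7 = 14% to 5/11 = 45%. With e at 20% and s at 1%, it is 1/21 = 5%. All of these rates are assumptions, since the documents give none. A reader might quote such a share as the extent of the problem, but it would only restate the inputs.

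This is a supplementary descriptive safety table with no test attached. Nothing in the efficacy analysis depends on it.

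**What to change.** Complete the sentence in SAP Section 9.3.7.1 and add one definition, for example:

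*The subset comprises participants whose worse-eye grade on a treatment was at least 1 at a post-baseline visit and higher than the baseline grade that Section 9 assigns for that treatment. Recovery is a most recent worse-eye grade equal to or lower than that baseline grade.*

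Referring to the baseline rule in Section 9 also covers its exception for children who return to SYD-101 0.03% as escape medication after Vehicle. If the threshold of 1 is kept, the stated aim should say that it excludes a rise from 0 to 0.5.

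The cost is one or two sentences in the SAP and one extra condition in the program. The grades are already collected, so no visits or data are added.

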9.3.8. Intraocular Pressure (IOP)

IOP will be measured with a tonometer per study site's standard operating procedures and results recorded in units of mmHg on the eCRF. For analysis, the frequency of increase greater than 10 mmHg from baseline to any post-baseline timepoint will be measured by treatment received at

the time of the increase. Participants will be counted under each treatment received. The average of the right and left eyes will be used for analysis.

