Descriptive statistics of the quantitative vital sign, BCVA, and IOP results will be presented by treatment group and study visit, as well as for the change from baseline at each visit. The baseline value is defined as the last non-missing value prior to the first dose of study drug. Categorical variables for biomicroscopy collection, ophthalmoscopy abnormalities, and responses to the tolerability questionnaire will be summarized by treatment group with counts and percentages of

participants in each category. Percentages will be based on the number of participants with relevant non-missing data at the visit of interest.

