Continuous data will be summarized by treatment group using descriptive statistics (number, mean, median, standard deviation (SD), minimum, and maximum). Categorical data will be summarized by treatment group using frequency tables (frequencies and percentages). Mean will be presented to one decimal place beyond the precision with which the data was captured. SD and median will be presented to two decimal places beyond the precision with which the data was captured. Minimum and maximum will be presented to the precision with which the data was captured. When count data are presented, the percentage will be suppressed when the count is zero in order to draw attention to the non-zero counts. A row denoted “Missing” will be included in count tabulations where specified on the shells to account for dropouts and missing values if needed. Unless otherwise noted, the denominator to determine the percentage of participants in each category will be based on the number of participants with available data. Select ordinal data may be summarized using both descriptive statistics and counts and percentages of participants in each category, as appropriate.

For measurements such as SE and axial length which are collected multiple times per eye, the per eye averages will be calculated from the available values for each eye and then the average value of the right and left eyes will be calculated. The average values will be presented as rounded to two decimal places in data listings, however no rounding will be performed prior to the final calculation of the average value for both eyes.

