9.3. Ocular Safety Data

9.3.1. Best Corrected Visual Acuity (BCVA)

Best-Corrected Visual Acuity (BCVA) will be measured in each eye prior to cycloplegia with the participant wearing current correction using the Early Treatment of Diabetic Retinopathy Study (ETDRS) testing protocol. If the vision is more than 1 line (≥ 5 letters) worse than baseline, the testing will be redone using trial frames or phoropter with the most recent subjective refraction.

Changes in BCVA will be summarized for the Safety Set and subgroups (Age, Sex, Race and Iris Color) based on the following categories:

- ≥ 15 letters gained
- ≥ 10 letters but < 15 letters gained
- ≥ 5 but < 10 letters gained
- No change (< 5 letters change)
- ≥ 5 but < 10 letters lost
- ≥ 10 but < 15 letters lost
- ≥ 15 letters lost

Shift in BCVA from baseline will be measured for most recent assessment (i.e., the last available assessment prior to or on the analysis cut-off of Month 24, Month 36, Month 48) and worst-post baseline assessment at Month 24, Month 36 and Month 48 for each treatment received. The average of BCVA from the right and left eyes will be used for analysis.

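### SAP 9.3.8 and 9.3.1 do not carry over the by-visit IOP and BCVA summaries that Protocol 9.4.4 requires, and the count that remains for IOP is insensitive to a modest systematic rise

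*SAP*

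**What the plan says.** Protocol 9.4.4 is explicit: "Descriptive statistics of the quantitative vital sign, BCVA, and IOP results will be presented by treatment group and study visit", and it continues "as well as for the change from baseline at each visit".

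The SAP, which says it is based on Protocol Version 3.0, is narrower.

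- **IOP (SAP 9.3.8).** One analysis is named: "the frequency of increase greater than 10 mmHg from baseline to any post-baseline timepoint will be measured by treatment received". It is applied to the mean of the two eyes: "The average of the right and left eyes will be used for analysis". No mean, change or visit table is mentioned.
- **BCVA (SAP 9.3.1).** "Changes in BCVA will be summarized for the Safety Set and subgroups (Age, Sex, Race and Iris Color) based on the following categories". Seven classes follow, with cuts at 5, 10 and 15 letters gained or lost. The section then says "Shift in BCVA from baseline will be measured for most recent assessment", and likewise for the worst post-baseline assessment, at each analysis cut-off.

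For other continuous measures the SAP writes the by-visit summaries out. For pupil diameter (SAP 9.3.4): "Descriptive statistics for pupil diameter and changes from baseline at each assessment time point will be presented by randomized treatment". SAP 9.2 (vital signs), 9.3.5 (accommodative amplitude) and 9.3.6 (endothelial cell density) do the same in similar terms.

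**The concern.** Changes from baseline in BCVA and IOP are listed safety endpoints in Protocol 3 and SAP 3.4. Protocol 9.4.4 names three measures for by-visit reporting: vital signs, BCVA and IOP. Only vital signs keep that reporting in the SAP section written for them.

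For IOP, what remains is an outlier screen. Children enter with IOP below 21 mmHg and receive nightly antimuscarinic drops for years. A count of rises above 10 mmHg can find individual large rises. It says little about whether a whole arm has moved up by a small amount. If the count is close to zero in every arm, a reader of the study report may take that as evidence that IOP is unaffected, and nothing else specified in the SAP section would correct that reading.

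**Working it through.** The plan gives no figure for this point, so there is none to reproduce. The check has two parts.

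**1. Does any other SAP text supply the by-visit tables?**

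- SAP 4, general convention: "Continuous data will be summarized by treatment group using descriptive statistics". This fixes the statistics, but promises no visit or change table for any particular measure.
- SAP 4, visit windows: these cover safety as well as efficacy, but only say how an assessment is assigned to a visit.
- SAP 6.1: descriptive statistics for IOP and BCVA, at baseline only.
- SAP 8: the rule to summarize by treatment and visit covers efficacy endpoints only.
- SAP 9, opening: safety is assessed through summaries of changes that include BCVA and IOP. No statistic or visit is named.
- SAP 11: neither IOP nor BCVA is mentioned.

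None of these fills the gap, and none declares it.

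**2. What can the stated summaries show?**

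*IOP inputs.* 280 per arm (SAP 4.1); threshold 10 mmHg (SAP 9.3.8); annual IOP at Months 12, 24 and 36 (schedule of activities). Assumed: normally distributed change, SD 2.5 to 3.5 mmHg, uniform shift d = 1 mmHg, and three independent measurements. With positively correlated visits the any-visit probability would be lower, so the counts below are on the high side.

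At one visit, p = 1 − Φ((10 − d)/SD). Over three visits, the expected count is 280 × [1 − (1 − p)³]. The standard error (s.e.) of a difference in mean change at one visit is SD × √(2/280) = SD × 0.0845.

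| SD (mmHg) | p, no shift | p, 1 mmHg shift | Expected count per 280, no shift v shift | s.e. of mean difference | Shift in s.e. units |
|---|---|---|---|---|---|
| 2.5 | 0.00003 | 0.00016 | 0.03 v 0.13 | 0.21 | 4.7 |
| 3.0 | 0.00043 | 0.00135 | 0.36 v 1.13 | 0.25 | 3.9 |
| 3.5 | 0.00214 | 0.00506 | 1.79 v 4.23 | 0.30 | 3.4 |

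A by-visit mean would show a 1 mmHg shift clearly, while the count differs by between a tenth of a child and about two and a half children per arm. With the 7% annual dropout used in SAP 4.1, about 280 × 0.93³ = 225 remain per arm at Month 36. The shift is then still 3.0 to 4.2 standard errors, and the counts are smaller.

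The contrast narrows for larger shifts. With SD 3 and a 5 mmHg shift, p = 1 − Φ(5/3) = 0.048, or about 13 of 280 at a single visit, against 0.1 without a shift.

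*BCVA inputs.* Assumed SD of change 4 to 6 letters, normal. Share losing at least 5 letters at one assessment = Φ((−5 + d)/SD), where d is the mean loss. Power is for 280 per arm at two-sided 0.05 and serves only as a gauge.

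| SD (letters) | No loss | 1-letter loss | 2-letter loss | Power, class, 1 letter | Power, mean, 1 letter | Power, class, 2 letters |
|---|---|---|---|---|---|---|
| 4 | 10.6% | 15.9% | 22.7% | 46% | 84% | 97% |
| 5 | 15.9% | 21.2% | 27.4% | 37% | 66% | 92% |
| 6 | 20.2% | 25.2% | 30.9% | 29% | 51% | 82% |

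A 2-letter loss raises that class by 11 to 12 percentage points, which is plain in a table. A 1-letter loss raises it by about 5 points and could be missed.

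**The case against.** The strongest reply is that nothing has been withdrawn. The SAP follows Protocol Version 3.0, keeps both measures as change-from-baseline safety endpoints, gives a convention for continuous data and defines change from baseline. SAP 4 also refers to table shells that are not in these documents, and the by-visit tables may be planned there. It is therefore fair to say that the summaries are not carried over; the documents do not show a deliberate removal. The gap in the SAP text remains, because a programmer working from 9.3.8 alone would produce only the count.

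Four stronger readings are tempting, and the documents do not support them.

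- *An acuity shift would go unseen.* The classes would show a loss of about 2 letters. The limit to the most recent and worst assessments is attached to the sentence on shifts; the sentence on classes names no timepoint.
- *The IOP count will be near zero whatever the drug does.* This fails for large shifts, as the 5 mmHg case shows. How rare such rises are rests on the assumed SD and not on any source in the documents.
- *The plan gives up a large amount of statistical power.* Protocol 9.4.4 asks for descriptive statistics. Neither document plans a test of IOP, so there is no planned power to lose.
- *IOP and BCVA were singled out.* Binocular near acuity (SAP 9.3.2) is also reported only in classes.

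**Conclusion.** The inconsistency stands and rests on the text alone: Protocol 9.4.4 requires by-visit values and changes for BCVA and IOP, the SAP sections for those measures do not provide them, and SAP 11 is silent.

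The consequence differs by measure. For IOP, the only stated summary is insensitive to a modest systematic rise: for a 1 mmHg shift, expected counts per 280 run from 0.03 v 0.13 to 1.8 v 4.2. This depends on the assumed SD of 2.5 to 3.5 mmHg, normality and independent annual measurements. The documents also do not say that 1 mmHg is clinically important. The supported conclusion is that a near-empty table should not be read as absence of an IOP effect. For BCVA, the loss is limited to the time course and the smallest shifts.

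This is a reporting gap of moderate weight that should be closed. Efficacy analyses and their error control are untouched.

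**What to change.** Add to SAP 9.3.8 and 9.3.1 the summaries in Protocol 9.4.4: n, mean, SD, median, minimum and maximum of the observed value and of the change from baseline, at each scheduled assessment, by treatment group. The wording in SAP 9.2 and 9.3.4 can be reused.

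State which grouping and baseline apply from Month 36. The opening of SAP 9 then groups by treatment being taken and generally resets baseline for each treatment, whereas 9.3.4 uses randomized treatment.

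Keep the count of rises above 10 mmHg and the letter classes as outlier displays. Between-arm differences with 95% CIs would help the reader, but they go beyond the protocol and are optional. If the sponsor prefers the present summaries, SAP 11 should record and justify the departure.

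Cost: two extra standard tables and a few lines of SAP text, with no new measurements.

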8.4. Quality of Life (QOL) Questionnaire

The investigator’s designee will administer a questionnaire to participants (or parents/guardians) to assess potential impact of treatment on the participant’s QOL. Responses will be marked as strongly agree, agree, neither agree or disagree, disagree, strongly disagree. There are eight questions in all. Questions 2 to 7 will be scored from 5 for strongly agree to 1 for strongly disagree and questions 1 and 8 will be reversed scored from 1 for strongly agree to 5 for strongly disagree so that higher values consistently indicate a “worse” outcome for the participant.

Summary statistics will be presented for each question as well as for the per participant average of the 8 questions. Participants will be included in the analysis of average question score if they have at least 4 non-missing question responses. For the average question score, missing question responses will be imputed from the mean of the available question responses.

Additionally, a Wilcoxon Rank Sum test and frequency tables will be presented summarizing

results and individual participants responses will be listed. The Wilcoxon Rank Sum test will be performed in a pairwise manner comparing each treatment dose (SYD-101 0.01%, SYD-101 0.03%) to vehicle. The ranks are based on the observations of the two groups that are compared, p-values from the exact Wilcoxon Rank Sum test as well as the Hodges-Lehman estimates ([Hodges, J. L.; Lehmann, E. L. \(1963\)](#)), and Moses 95% CI ([Moses, Lincoln E. \(1965\)](#)) will also be presented for supportive use. No adjustment for type 1 error will be made for the multiple dose comparisons or multiple timepoints.

9. Safety Analysis

Safety will be assessed through summaries of AEs and changes in vital signs, BCVA, biomicroscopy, IOP, and ophthalmoscopy abnormalities. Safety data will be summarized by treatment group using the Safety Set.

In general, for ocular assessments, safety will be summarized using the average of both eyes averages, with a few exceptions where presenting data for the eye with the worse response for the given assessment. Percentages, if applicable, will be calculated based on the number of participants in the Safety Set. For analysis of event data, participants will be counted once for given event if the event occurs in at least one eye.

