9.3.3. Dilated Ophthalmoscopy

An ophthalmoscopy examination will be performed with pupil dilation using an indirect ophthalmoscope as per the current standard of practice to evaluate the condition of the vitreous, macula, retina, optic nerve, choroid, and retinal periphery.

Ocular findings will be evaluated by the following criteria:

- Normal
- Abnormal (not clinically significant [NCS])
- Abnormal with clinical significance (clinically significant [CS])

The number and percentage of participants with at least 1 treatment-emergent clinically significant abnormality for any parameter and for each parameter will be summarized for each treatment group. At each level of summarization, a participant will be counted once even if the participant experiences more than one treatment-emergent clinically significant abnormality summarizing data for the worse eye. For analysis, the worse eye will be defined as the eye with the greater degree of abnormality where Abnormal CS > Abnormal NCS > Normal. An abnormality will be deemed treatment emergent if the onset date is on or after the date of first treatment. Data from all ophthalmoscopy assessments will be listed.

At Month 36 and Month 48 analyses, findings will be summarized for participants by current treatment at time of abnormality.

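### The IOP and BCVA threshold tables use only the two-eye average, so a large one-eye change can go uncounted or fall in a milder class; adding either-eye and worse-eye tables is a cheap improvement

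*SAP*

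**What the plan says.** SAP 9.3.8 (Intraocular Pressure) tabulates "the frequency of increase greater than 10 mmHg from baseline to any post-baseline timepoint", counts participants under each treatment received, and adds: "The average of the right and left eyes will be used for analysis". SAP 9.3.1 (BCVA) uses seven classes, from gains of 15 letters or more to losses of 15 letters or more. The middle class is labelled "No change (< 5 letters change". The table is made for the most recent and the worst post-baseline assessment, and "The average of BCVA from the right and left eyes will be used for analysis". Neither section adds a per-eye or worse-eye table.

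The opening of SAP section 9 makes averaging the default: "In general, for ocular assessments, safety will be summarized using the average of both eyes averages, with a few exceptions". It also says: "For analysis of event data, participants will be counted once for given event if the event occurs in at least one eye". It does not say whether an IOP rise above 10 mmHg is event data.

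Other ocular safety sections use the worse eye. In 9.3.3 (ophthalmoscopy) "the worse eye will be defined as the eye with the greater degree of abnormality". In 9.3.7 (biomicroscopy) "a participant will be counted once even if the participant experiences more than one treatment-emergent clinically significant abnormality summarizing data for the worse eye". In 9.3.7.1 (corneal staining) the eye with the higher grade is used. SAP 9.3.2 (near acuity) also states a worse-eye rule, although that test is binocular, so it carries less weight as a precedent.

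**The concern.** A threshold table answers a different question from a table of means: how many children had a change this large. IOP and acuity are properties of each eye. Averaging a changed eye with an unchanged one halves the change before it meets a threshold that is the same size as it would be for a single eye. The two-eye mean already has a natural place in the by-visit IOP and BCVA descriptive statistics of protocol 9.4.4. In the threshold tables it leaves a blind spot for one-eye changes.

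At stake is the completeness of two between-arm safety tables in a paediatric trial of up to 48 months.

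**Working it through.** The documents give no expected count for these tables, so there is no planned figure to reproduce. The check applies the SAP's own rules and then adds an illustration with assumed inputs.

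**1. Exact arithmetic, fellow eye unchanged.** Analysed change = (right change + left change) / 2.

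IOP, counted only if the mean exceeds 10 mmHg:
- One eye +15: 15/2 = 7.5, not counted.
- One eye +20: 20/2 = 10.0, not counted. Inclusion criterion 11 requires IOP below 21 mmHg in both eyes, so an eye going from 20 to 40 mmHg beside a stable fellow eye would be absent from the table.
- One eye +21: 21/2 = 10.5, counted.

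A mean above 10 requires at least one eye above 10, so the averaged count can never exceed the either-eye count.

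BCVA:

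| One-eye loss (letters) | Mean loss | Class by mean | Class by worse eye |
|---|---|---|---|
| 5 to 9 | 2.5 to 4.5 | no change | 5 to <10 |
| 10 to 14 | 5 to 7 | 5 to <10 | 10 to <15 |
| 15 to 19 | 7.5 to 9.5 | 5 to <10 | 15 or more |
| 20 to 29 | 10 to 14.5 | 10 to <15 | 15 or more |
| 30 | 15 | 15 or more | 15 or more |

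**2. Illustration for IOP.** Assumptions, none from the documents: bivariate normal changes, per-eye SD σ of 3 to 5 mmHg, between-eye correlation ρ of 0.3 to 0.9. The documents supply the threshold of 10 and the 280 per arm.
- Average rule: P = 1 − Φ((10 − mean change) / (σ√((1+ρ)/2))).
- Either-eye rule: P = 1 − Φ₂(10, 10), the bivariate normal probability that at least one eye exceeds 10.

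Worked case, σ = 4 and ρ = 0.7. The SD of the mean is 4√0.85 = 3.69.
- No true change: average 1 − Φ(10/3.69) = 0.00335, or 0.94 per 280 per visit; either-eye 0.01093, or 3.06 per 280.
- True rise of 15 mmHg in one eye and 0 in the other: average 1 − Φ((10 − 7.5)/3.69) = 0.249; either-eye 0.894.

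Over the whole assumed range, the average rule counts 15 to 30% of children with such a one-eye rise and the either-eye rule 84 to 95%. Chance crossings per 280 per visit, either-eye against average, are 0.2 against 0.0–0.1 (SD 3), 2.6–3.4 against 0.3–1.4 (SD 4) and 9.0–12.2 against 1.8–5.6 (SD 5).

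SAP 9.3.8 counts a rise at any post-baseline timepoint, so chance crossings accumulate. Over three annual IOP visits (assuming a shared baseline and equal variance at each visit) they are about 7–9 against 1–4 per 280 at SD 4, and 22–30 against 5–14 at SD 5.

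**3. Which rule separates the arms better?** Compare the between-arm gap divided by its standard error, √(p₁(1−p₁)/280 + p₀(1−p₀)/280), at σ = 4 and ρ = 0.7:
- Uniform 2 mmHg shift in both eyes of one arm: gap 7.62 (either-eye) against 3.27 (average) per 280; ratio to SE 2.09 against 1.45.
- 3% of one arm rising 15 mmHg in both eyes: gap 7.89 against 7.64; ratio 2.14 against 2.51.

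Over the 12 SD and correlation combinations, the either-eye rule has the larger ratio in all 12 for the uniform shift. The average has it in all 12 for the few large two-eye rises, with a small margin at SD 3.

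**4. Worse-eye BCVA classing with no true change** (assumed SD 5 letters, ρ 0.3 to 0.9). Losses of 5 letters or more appear in 20–27% and gains in 5–12%; the average gives 11–15% for each. Classing everyone by the worse eye would therefore inflate losses and suppress gains.

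**The case against.** The strongest reply is that the averaging is deliberate and the practical loss small. Section 9 declares it, and measured quantities such as pupil diameter, endothelial cell density, IOP and BCVA follow it. The worse-eye sections mostly concern ordinal ratings and grades, which do not average well. Every child receives a drop in each eye, so drug effects should mostly be two-eyed. Protocol section 3 and 8.2 send clinically significant findings to the AE record, SAP 9.1.1 counts an AE in either eye, and raw data are listed. A BCVA loss of 5 letters or more triggers a retest, and SAP section 4 uses a same-day retest for analysis.

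All of this stands and limits the point. It does not remove it. Protocol 8.3.5 sets an AE grade for corneal staining but none for an IOP rise or a letter loss, so AE capture rests on investigator judgement. Neither AE records nor listings correct the threshold tables.

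Two stronger readings are tempting. A reader might infer that the SAP breaks its own either-eye rule. The documents do not support that: averaging is the stated default, and the IOP count is not declared to be event data. A reader might also infer that the either-eye rule is simply better and should replace the average. Steps 3 and 4 of the working do not support that: the better rule depends on the form of the effect, and worse-eye classing distorts a table that also shows gains.

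**Conclusion.** The point holds as a cheap improvement, between optional and recommended. The one-eye blind spot follows exactly from the SAP's rules when the fellow eye is unchanged, and needs no assumption. How many children it would hide cannot be derived from the documents, because they give neither the SD of change nor the between-eye correlation; the number may be very few. The either-eye rule is the more sensitive for one-eye rises or small uniform two-eye shifts, and the average for a few children with large two-eye rises. That is a reason to show both. No efficacy conclusion or error rate changes.

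A minor wording matter lies beside it. SAP 9.3.4 and 9.3.5 present pupil diameter and accommodative amplitude by randomized treatment at every time point, but active-arm participants are randomized twice and some move to escape medication. SAP section 9 allows sections to specify their own grouping, so this is not an error, and SAP Table 7-1 suggests that the initial arm is meant. On that reading the columns after Month 36 no longer compare drug with vehicle: the Vehicle arm is assigned 0.03% and half of each active arm is assigned Vehicle. Data to Month 24 are unaffected, and later efficacy and safety summaries after Month 36 are exploratory.

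**What to change.** Keep the averaged tables and the two-eye means. Add:
- in SAP 9.3.8, the number of participants with an IOP rise above 10 mmHg in either eye;
- in SAP 9.3.1, a loss-only table by the worse eye (5 or more, 10 or more, 15 or more letters), leaving gains as they are.

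Note with both that they are to be read as between-arm comparisons, because chance crossings will be more frequent in every arm and will accumulate over visits.

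As a clarification, state in 9.3.4 and 9.3.5 that randomized treatment applies to data before escape or Month 36, and group later data by initial and current treatment as SAP section 4 already does.

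The cost is SAP wording and minor programming. Both eyes are measured at every eye assessment and treatment changes are recorded, so no new data are needed. The later groups in 9.3.4 and 9.3.5 become smaller.
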